1. BACKGROUND AND RATIONALE

Surgery has been associated with short and long-term changes in cognition (postoperative cognitive dysfunction, POCD).^{1,2} The literature shows that most often patients show POCD during the first 1-3 months after surgery, and then recover.³ However, in the recently published NeuroVISION study, up to 30% of 65 years old or older people undergoing different types of noncardiac surgery presented a decline of ≥ 2 points in their Montreal Cognitive Assessment (MoCA) score at 1 year after surgery compared to prior to surgery.⁴ A ≥ 2 points in MoCA score has been shown to correspond to cognitive decline based on formal neuropsychological testing and to be of clinical significance.^{5,6} The risk factors and determinants of POCD are poorly understood.⁷

Chronic pain has been associated with cognitive dysfunction, in particular memory and concentration deficits.⁸ The existing literature on chronic pain in general supports the hypothesis of a bidirectional interaction between pain and cognitive processing.⁸ However, in a longitudinal community-based study, a history of persistent pain (of any origin) at baseline was associated with memory decline, and even dementia, over 10 years of follow-up.⁹ We hypothesize that a similar association might exist between post-surgical pain, and in particular chronic post-surgical pain (CPSP) and POCD (**objective 1**). A surgical population including older ages and with an expected high prevalence of CPSP, like patients undergoing total knee and hip replacement,¹⁰ seems a suitable population to evaluate this association. In this population, up to 23% of hip replacement and 34% of knee replacement surgery patients experience long term pain after surgery.¹¹ The long-term need of analgesic therapy, and in particular, the chronic use of opioids in patients with CPSP, could also play an independent role in mediating the association between CPSP and cognitive changes. Overall, the existing literature on the association between CPSP and POCD, including the role of long-term opioid use, is very scanty and controversial.¹¹⁻¹³

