2. OBJECTIVES

The overarching objective of the ArthroCaP study is to explore the interplay between postoperative pain and self-reported recovery (i.e. satisfaction), coping abilities/expectations about surgery, and postoperative COGNITIVE trajectories in ≥ 50 years old people undergoing elective total knee arthroplasty (TKA) or total hip arthroplasty (THA).

The specific objectives of the ArthroCaP study are:

1. to explore the association of CPSP, long-term opioid use, and a multi-domain measure of patient satisfaction, with POCD, measured as changes over time of the performance at the Montreal Cognitive Assessment (MoCA) score, and at additional neuropsychological testing.
2. to explore whether postoperative cognitive changes are associated with changes in neurogenesis correlates (a) and in neurotrophic factors levels (b), and whether this association is mediated by changes in pain, mobility, and satisfaction
3. to explore the association between coping strategies/expectations before and after surgery, as measured by the SPOC questionnaire, and cognitive changes after surgery; and to explore the correlation between changes in SPOC and cognitive changes from preoperative to 4-6 weeks after surgery.
4. to qualitatively explore lived experiences of pain, mobility and aging, including resilience, expectations and satisfaction with surgery, in patients undergoing TKA or THA across different ages and comorbidities.

The current protocol and ethics submission describes methods and seek ethics approval for specific objectives 1-3. Objective 4 will be covered in a separate protocol and ethics application.

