3.4 Measurements

Patients who agree to participate in the ArthroCaP sub-study while the recruitment in SPOC is ongoing will undergo all the procedures and measurements outlined in the protocol for the main study. In particular, participants are assessed at baseline for their socio-demographics data, comorbidities, Physical Frailty Phenotype, health-related quality of life (EQ-5D), anxiety and depression (Hospital Anxiety and Depression Scale [HADS]), pain, and pain medication. Pain scores (based on a numerical pain scale) and pain medications are assessed at baseline, and then 4-6 weeks, 3 months, 6 months and 12 months after surgery. The SPOC instrument is administered at baseline and repeated at 4-6 weeks after surgery. The presence and severity of CPSP and satisfaction (SAPS) are measured at 3, 6, and 12 months. Changes in health-related quality of life and clinical complications are also monitored and collected over time. For TKA and THA patients approached after the termination of the recruitment in SPOC, these measurements will be described in the ArthroCaP informed consent form and conducted by the ArthroCaP study team

using ArthroCaP-specific case report forms (CRFs), as done for the cognitive/neuropsychological assessment.

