3.6 Statistical analyses

Baseline characteristics will be summarized through descriptive statistics, i.e. mean (standard deviation), median (interquartile range [IQR]), or number (%) as appropriate.

Objective 1. We will first evaluate the primary study objective modeling longitudinal changes in pain scores (independent variable) and changes in cognitive/neuropsychological scores (dependent variable) over time (4 weeks, and 3, 6, and 12 months after surgery) using multilevel (mixed effects) regression models, considering time points nested within patients.³⁶ Secondly, in mixed effects models, we will specifically look at whether experiencing moderate-severe persistent pain at 3 months after surgery (or at 6 months after surgery) predicts subsequent decline in cognitive performance (i.e. at 6 and 12 months, or at 12 months).⁹ Models will be adjusted for relevant covariates, including baseline characteristics (at the patient level, e.g. age, sex, comorbidity index, and anxiety/depression level) and pain medications as time-varying variables. We will adopt a parsimonious approach in covariates selection, based on clinical relevance and removing collinear covariates (i.e., variance inflation factor > 2.5) according to pre-specified priorities. We will use the same statistical approach to look at the association between satisfaction (measured with the SAPS instrument) and cognitive performance.

Objectives 2. We will explore our objective 2a, analyzing separately change in MST scores and changes in other cognitive performance measures. Bonferroni correction of alpha values will be adopted to adjust for multiple comparisons. For the biomarker study (objective 2b), we will similarly model mixed effects regression models to evaluate how the biomarker levels change over time and how these changes correlate with changes in pain, satisfaction, and cognitive performance. We will also analyze whether biomarkers levels at baseline (before surgery), and

right after surgery (or at 4-6 weeks after surgery) predict cognitive changes/decline at 6 and 12 months.

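### The objective 1 models condition on postoperative pain medication, a possible mediator named in the background, and no objective 1 model without it is planned, so the total association of chronic post-surgical pain with cognition has no pre-specified estimate

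*Combined protocol and SAP*

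**What the plan says.** Section 2 sets objective 1 as "to explore the association of CPSP, long-term opioid use, and a multi-domain measure of patient satisfaction, with POCD" (POCD is postoperative cognitive dysfunction). Section 1 suggests how drugs may enter: lasting analgesic use, and opioids in patients with CPSP in particular, "could also play an independent role in mediating the association between CPSP and cognitive changes".

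Section 3.6 describes two sets of mixed models for objective 1. The first relates pain scores over time to cognitive scores over time. The second asks whether "experiencing moderate-severe persistent pain at 3 months after surgery (or at 6 months after surgery) predicts subsequent decline in cognitive performance", with cognition at 6 and 12 months (or at 12 months) as the outcome. The adjustment sentence follows both sets and exempts neither: "Models will be adjusted for relevant covariates, including baseline characteristics", with examples, "and pain medications as time-varying variables". Section 3.4 states that "pain medications are assessed at baseline, and then 4-6 weeks, 3 months, 6 months and 12 months after surgery", and Appendix I agrees, so the covariate includes postoperative values.

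Section 3.6 describes no objective 1 model with baseline covariates only, and no analysis that splits the CPSP association into a part through medication and a remainder.

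**The concern.** Medication taken because pain persists comes after the exposure. If it affects cognition, holding it fixed takes that pathway out of the pain coefficient. What remains is the association among patients with the same treatment, which is a different quantity from how far cognition differs between patients with and without CPSP.

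Both quantities are of interest, but the plan provides only one and does not say which it is. A weak pain coefficient could then be read as a weak link between CPSP and cognition when part of the link runs through treatment. Section 4 says that the study will give preliminary data on the role of both chronic pain and chronic pain medication, and will inform larger studies and interventions. Later planners would need to know which association each estimate describes.

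**Working it through.** **Timing.** The plan states no figure on this point, so the first check is the order of measurement in Appendix I.

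- Exposure at 3 months: the outcome is cognition at 6 and 12 months. Medication at 6 and 12 months enters as a covariate and is recorded after the exposure.
- Exposure at 6 months: the outcome is cognition at 12 months. Medication at 12 months is recorded after the exposure.
- Pain scores over time: pain and medication are recorded at the same visits, so medication can be a consequence of earlier pain and also a cause of later pain scores and cognition.

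**Would the covariate rule remove medication?** Section 3.6 plans "removing collinear covariates (i.e., variance inflation factor > 2.5) according to pre-specified priorities". A variance inflation factor (VIF) above 2.5 needs R² above 1 − 1/2.5 = 0.60. Take CPSP prevalence B = 30% (section 3.5) and assumed opioid use q1 with CPSP and q0 = 10% without. Overall use is m = B·q1 + (1 − B)·q0. Between the two variables alone, R² = B(1 − B)(q1 − q0)² / [m(1 − m)].

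- q1 = 30%: m = 0.16, R² = 0.0084/0.1344 = 0.06, VIF = 1.07.
- q1 = 50%: m = 0.22, R² = 0.0336/0.1716 = 0.20, VIF = 1.24.
- q1 = 70%: m = 0.28, R² = 0.0756/0.2016 = 0.375, VIF = 1.60.

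On these values medication stays in the model. Other covariates could raise the VIF, but a removal that depends on the data would still not be a planned analysis.

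**Size, on assumed inputs.** The documents give no opioid-use rates and no effect sizes. For a linear model without interaction:

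- indirect part = (q1 − q0) × opioid effect
- total = direct effect + indirect part
- share missing from the adjusted coefficient = indirect part / total

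| Opioid use with / without CPSP | Opioid effect (MoCA points) | Direct CPSP effect (points) | Indirect part | Total | Share missing |
|---|---|---|---|---|---|
| 30% / 10% | 0.5 | 1.0 | 0.10 | 1.10 | 9% |
| 30% / 10% | 1.0 | 1.0 | 0.20 | 1.20 | 17% |
| 30% / 10% | 1.0 | 0.5 | 0.20 | 0.70 | 29% |
| 50% / 10% | 1.0 | 1.0 | 0.40 | 1.40 | 29% |
| 50% / 10% | 1.0 | 0.5 | 0.40 | 0.90 | 44% |

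Outside that range, 70% use with CPSP, an opioid effect of 1.0 and a direct effect of 0.5 give 0.60/1.10 = 55%. With no direct effect the share is 100% whatever the other values.

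**The case against.** **The target may be intended.** Section 2 lists CPSP and opioid use side by side, section 1 hedges the mediation idea and also gives opioids an independent role, and the objective does not ask for an overall or total association. A joint model is a legitimate reading, and it yields two coefficients: pain given medication, and medication given pain. This stands. It would be wrong to infer that the plan cannot separate pain from drugs. What has no planned estimate is the total, and the plan does not label the coefficient it does produce.

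**Medication may be a confounder.** Medication can influence later pain scores and cognition. A patient whose pain is controlled on opioids counts as low-pain, so leaving medication out could pull the pain estimate towards zero if opioids impair cognition. This stands for the repeated pain-score model, and it is why dropping medication everywhere is not the answer.

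**The total is not wholly absent.** Section 1, in the rationale for objective 2a, envisages correlating pain change and CPSP incidence with cognitive tests and states no adjustment set. That is not an objective 1 model, but a reader who infers that no medication-free association could ever appear goes beyond the text.

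**Satisfaction.** Section 3.6 says "We will use the same statistical approach to look at the association between satisfaction", so one might carry the same criticism over. The mediation statement in section 1 concerns CPSP only, and nothing in the documents places analgesics downstream of satisfaction.

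**Conclusion.** The point holds for pain and CPSP: the planned coefficient is conditional on treatment, and no objective 1 model estimates the total association. The case is strongest for the models with pain at 3 or 6 months as exposure. In the repeated pain-score model medication may be mediator and confounder at once, so neither version is definitive alone.

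The size cannot be known from the documents. The 9-44% rests on the assumed inputs, on linearity without interaction, on no unmeasured confounding between medication and cognition, and on opioids and pain acting in the same direction. If medication helped cognition, the adjusted coefficient would overstate the total instead.

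A reader might infer that the study will find CPSP irrelevant. The documents do not support that. On the assumed range 56-91% of the total remains, near-complete loss needs a direct effect close to zero, and section 3.5 presents the study as exploratory and preliminary, with no rule that turns a null coefficient into a conclusion. This is a problem of target and interpretation, not of error rates.

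**What to change.** In section 3.6, for the models with moderate-severe pain at 3 or 6 months as exposure:

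1. Pre-specify a model that adjusts for baseline covariates and preoperative pain medication, with no medication recorded after the exposure. Label it the total association.
2. Report it alongside the planned model with time-varying medication, and label that one the association conditional on treatment.

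For the repeated pain-score model, report both versions and state that medication may be both mediator and time-varying confounder, so that neither is definitive alone.

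No change to the satisfaction models is required. Nor is a table crossing pain with opioid use: at 100 patients, 30% CPSP and the assumed 10% use without CPSP, it would hold about 100 × 0.70 × 0.10 = 7 low-pain opioid users before dropout.

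The cost is a few sentences and one extra model per outcome. Preoperative medication is already collected. The downside is one more set of exploratory estimates.

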The presence of pain, and in particular joint pain, can significantly interfere with mobility, and an impaired physical performance can eventually affect the cognitive performance.¹⁴ The Self-Administered Patient Satisfaction (SAPS) Scale is used as a more comprehensive measure of patient recovery after surgery, since it includes the overall satisfaction with surgery, self-reported extent of pain relief, and ability to perform home or yard work, and recreational activities.¹⁵ Therefore it is also plausible to hypothesize an association of patient satisfaction (as measured by the SAPS) after surgery with long-term cognitive changes (**objective 1**).

Mechanisms with which postoperative pain and satisfaction could affect postoperative cognitive changes are unclear. One interesting hypothesis is that pain and satisfaction might interact with cognitive abilities through neurogenesis interference (**objective 2.a**).⁸ This would be similar to what is observed in depression.^{16,17} Numerous studies in animals have linked depression with hippocampal-reduced neurogenesis. In rodents, reduced neurogenesis is both a consequence of chronic stress exposure, and a vulnerability that predisposes animals to develop depressive symptoms when later subjected to stress.¹⁸ In the absence of a non-invasive measure of neurogenesis in humans, correlational evidence in human studies has identified several high interference memory tests (like the Mnemonic Similarity Test [MST]) as putatively neurogenesis-sensitive, because they are similarly impacted by factors that alter neurogenesis levels in rodents.^{19,20} In humans, deficits on the MST are associated with elevated scores on scales of

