stress, depression and binge drinking, and with increased age, while several weeks of high intensity exercise improve MST scores.^{21 22} Even if 30% of the NeuroVISION participants presented a decline of ≥ 2 points in their Montreal Cognitive Assessment (MoCA) score at 1 year, many participants experienced no changes or an improvement in their MoCA scores. To assess the role of neurogenesis in the association between CPSP and POCD, we can assess the correlation between changes in pain scores (and incidence of CPSP) with the MST, and separately with other cognitive/neuropsychological testing. According to the neurogenesis theory, as demonstrated in depressed patients recovering from their depressive state,¹⁷ we might see improved MST scores in patients who experience a postoperative improvement in their pain while still showing a postoperative decline in other cognitive domains/tests; and *vice versa*, patients with CPSP might show worsened MST scores, without showing significant changes in other cognitive tests/domains. Neurotrophic factors support the survival and function of hippocampal cells. Neurotrophic like the brain-derived neurotrophic factor (BDNF) and the insulin-like growth factor-1 (IGF-1) have been shown to enhance the association between higher aerobic fitness and better memory performance.²³ Conversely, a reduction in neurotrophic factors might mediate the interaction of pain, reduced mobility and satisfaction, with cognition (**objective 2.b**).

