We will measure longitudinally the levels of neurotrophic factors that have showed promising results as possible mediators of the effect of physical performance (and, we hypothesize, pain and satisfaction), on neuroplasticity (and possibly cognitive performance), i.e. the *brain-derived neurotrophic factor* (BDNF) and the *insulin-like growth factor-1* (IGF-1).²³ We will include the measurement of the *nerve growth factor* (NGF), another neurotrophic factor that has been associated with neuron survival and cognitive performance.³⁴ We will also measure NT-proBNP. Preoperative NT-proBNP levels have been demonstrated to be a strong independent predictor of major postoperative outcomes after non-cardiac surgery.³⁵ However, the role of NT-proBNP in predicting postoperative cognitive outcomes has been not assessed. Moreover, NT-proBNP is usually measured preoperatively whereas the dynamic changes of its perioperative and postoperative levels, and their correlation with postoperative outcomes, have never been evaluated. Interestingly, NT-proBNP has been shown to correlate with measures of physical performance and tolerance (like peak oxygen consumption, VO₂ peak) which could be affected by persistent pain and could affect satisfaction. We will explore how the changes on NT-proBNP also correlate with changes in pain and satisfaction, as well as with changes in neurotrophic factors levels.

We will measure the plasma levels of neurotrophic factors but also their RNA expression in blood leukocytes. For participants who agree to have their blood samples stored in the biobank and also to have their genetic material tested, we will explore other mechanistic hypotheses and other possible biomarkers in the field of CPSP and POCD from plasma but also RNA expression and DNA.

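### Objective 2 is only partly answered by section 3.6: no model links MST change to cognitive change, the mediator's direction is contradictory, and no mediation analysis is planned

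*Combined protocol and SAP*

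**What the plan says.** Section 2 states objective 2 in two parts. The first is an association: "to explore whether postoperative cognitive changes are associated with changes in neurogenesis correlates (a" (the letter marks 2a), with neurotrophic factors as 2b. The second is "whether this association is mediated by changes in pain, mobility, and satisfaction".

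The mechanism is described elsewhere. Section 1 suggests for 2a that "pain and satisfaction might interact with cognitive abilities through neurogenesis interference", and for 2b that "a reduction in neurotrophic factors might mediate the interaction of pain, reduced mobility and satisfaction, with cognition". Section 3.4.2 calls the neurotrophic factors "possible mediators of the effect of physical performance (and, we hypothesize, pain and satisfaction), on neuroplasticity (and possibly cognitive performance".

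On analysis, section 1 proposes to "assess the correlation between changes in pain scores (and incidence of CPSP) with the MST, and separately with other cognitive/neuropsychological testing". Section 3.6 carries this over for 2a: "We will explore our objective 2a, analyzing separately change in MST scores and changes in other cognitive performance measures", with Bonferroni correction. For 2b it plans mixed models relating biomarker change to change in pain, satisfaction and cognition, and prediction of 6- and 12-month cognition from baseline and early postoperative biomarker levels.

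**The concern.** A reader who follows section 3.6 exactly finishes with results for MST and results for the other tests, but none that says whether the two move together, which is the question 2a puts. Nor would there be any estimate for the mediation clause, and the documents do not agree on which variable is the mediator.

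Section 4 says the study's data on mechanisms will inform larger confirmatory work. If the direction stays open, it can be chosen after the results are seen, and a later study could inherit a mechanism that was never estimated.

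**Working it through.** The documents give no figure for objective 2, so there is none to reproduce. Steps 1, 2 and 4 are a reading; steps 3 and 5 use assumed effect sizes and are illustrative.

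**1. Association.**
- 2a, section 2: cognitive change against MST change. Section 3.6: the two analysed separately. There is no linking model.
- 2b, section 2: cognitive change against neurotrophic factor change. Section 3.6: mixed models that include this pair. This part is covered.

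**2. Direction of mediation.**
- Section 2: marker → pain, mobility or satisfaction → cognition.
- Section 1, for 2a: pain or satisfaction → neurogenesis → cognition.
- Section 1, for 2b: pain, reduced mobility or satisfaction → neurotrophic factors → cognition.
- Section 3.4.2: physical performance (by hypothesis also pain and satisfaction) → neurotrophic factors → neuroplasticity, and possibly cognition.
- Section 3.6: no indirect effect in either direction, for 2a or 2b. Pairwise change models do not give one.

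**3. Why direction matters.** Assume pain → marker = −0.5, marker → cognition = 0.4, and no direct path.
- Marker as mediator: total pain effect = −0.5 × 0.4 = −0.20; direct effect = 0; mediated share = 100%.
- Pain as mediator: total marker association = 0.40; after adjustment for pain it is still 0.40; mediated share = 0%.

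A simulation of one million records gave 99.6% and 0.1%.

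**4. What is collected (3.4, 3.4.2, Appendix I).**
- Pain: baseline, 4-6 weeks, 3, 6 and 12 months.
- MST and the other tests: baseline, 4-6 weeks, 6 and 12 months.
- SAPS: 3, 6 and 12 months, with no baseline.
- Blood: before surgery and 2-4 hours after in every biomarker participant; tentatively at 4-6 weeks, when at least 50% attend in clinic; at 6 months in a possible subset; at 12 months in an expected 80% or more.
- Mobility: no measure named in 3.6 or Appendix I. SAPS covers home or yard work and recreation (section 1), so it is the closest repeated functional measure. Section 3.4 also follows health-related quality of life, but without visit times, and Appendix I omits it.

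**5. Precision and power.**
- 2a association at one time point, assuming r = 0.20 and n = 100: Fisher z = 0.203 ± 1.96/√97 = 0.203 ± 0.199, so the 95% interval for r is about 0.00 to 0.38.
- Indirect effect, both paths assumed 0.3, no direct effect, both tests required significant at two-sided 0.05. First path: z = 0.3095 × √(n−3). Second path: partial correlation (0.3 − 0.3 × 0.09)/√[(1 − 0.09)(1 − 0.0081)] = 0.287, so z = 0.2957 × √(n−4). Power is approximately the product of Φ(z − 1.96) over the two paths:

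| n | path 1 | path 2 | product | simulation |
|---|---|---|---|---|
| 30 | 0.363 | 0.326 | 11.8% | 11.6% |
| 50 | 0.564 | 0.518 | 29.2% | 29.7% |
| 80 | 0.775 | 0.732 | 56.7% | 57.0% |
| 100 | 0.862 | 0.826 | 71.2% | 71.7% |

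With the target of 100, blood at 4-6 weeks in 50% means 0.5 × 100 = 50 patients, fewer after separate biomarker consent.

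**The case against.** The best defence is that the plan is coherent on its own terms. Section 1 announces separate correlations and 3.6 delivers them. The objective 1 models relate pain to the cognitive and neuropsychological scores, and 3.4.1 lists MST among these, so the pain-MST association can be obtained. Section 1 also describes pain and cognition as acting on each other, so two directions are not incompatible in principle. Section 3.5 declares the study exploratory. All of this stands and lowers the severity. It does not supply the association that section 2 asks for, or say which direction is to be estimated.

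Four stronger readings are tempting, but the documents do not support them.

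- *Separate testing produces many false dissociations.* Section 1 predicts that "we might see improved MST scores in patients who experience a postoperative improvement in their pain while still showing a postoperative decline" on other tests, and 3.6 does not estimate that difference. But no passage gives a rule for reading the separate results. Assume n = 100, six tests at alpha 0.05/6, equal true correlations from 0 to 0.40 with pain, and residual correlation 0.3-0.5. MST alone significant among all six then occurs in at most 5% of studies, about the rate at which a direct contrast rejects. The figure is 13-20% (at r = 0.20-0.30) only if MST is compared with one given test.
- *The section 1 direction cannot be studied without 6-month blood.* Baseline pain, 4-6-week blood, then 6- and 12-month cognition is already time-ordered.
- *Nothing functional is measured.* SAPS has functional items.
- *The MST score is undefined.* Section 3.6 does not name one, but 3.4.1 identifies the lure discrimination index as the measure of mnemonic discrimination, which largely settles it.

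**Conclusion.** The point holds in a limited form, and a correction should be made. Three gaps can be seen by reading alone: the 2a association has no model; section 2 and sections 1 and 3.4.2 name opposite mediators, with no mediation analysis in either direction; and mobility is a named mediator without a named measure. A reader might infer that objective 2 as a whole goes unanswered. That is too strong, because the 2b associations are planned.

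Severity is modest, since the study claims only preliminary data. The mediated shares and power figures rest on assumed path sizes and show only that direction changes the answer and that few samples would give little power. The protocol of the main SPOC study, which may name further measures, was not available.

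**What to change.** 1. For 2a, keep the separate analyses and add an exploratory mixed model of change in each other test (MoCA, PAL, RVP, N-back, Stroop) on change in the MST lure discrimination index, with 95% confidence intervals. State whether these models fall inside or outside the Bonferroni family.
2. State one mediation direction consistently in sections 1, 2 and 3.4.2. Then either delete the mediation clause and claim association only, or pre-specify one exploratory indirect effect with a bootstrap interval along a time-ordered chain, reporting the number of samples used. Examples are baseline or 4-6-week pain, then 4-6-week MST or blood (exposure measured no later than mediator), then 6- and 12-month cognition; or perioperative or 4-6-week marker, then 3-month pain or SAPS, then 6- and 12-month cognition. SAPS enters as a level, not as a change from before surgery.
3. Delete mobility, or name the collected measure that stands for it.
4. State that non-significance on the other tests will not be read as absence of change.

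Optional: one contrast, on standardised scores, of the pain association with MST against that with the other tests. The gain is an interval for the difference predicted in section 1, not the removal of a large error rate.

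Cost: changes of wording, five association models and, if kept, one indirect effect and one contrast. No new data are needed. The downsides are more exploratory output and low mediation power where samples are few.
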